## 6. EXPECTED TOXICITIES AND DOSING DELAYS/DOSE MODIFICATIONS

Dose delays and modifications will be made using the recommendations in this section of the protocol. Toxicity assessments will be done using the CTEP Version 4.0 of the NCI Common Terminology Criteria for Adverse Events (CTCAE) which is identified and located on the CTEP website at:

[http://ctep.cancer.gov/protocolDevelopment/electronic\\_applications/ctc.htm](http://ctep.cancer.gov/protocolDevelopment/electronic_applications/ctc.htm).

If possible, symptoms should be managed symptomatically. In the case of toxicity, appropriate medical treatment should be used (including anti-emetics, anti-diarrheals, etc.).

All adverse events experienced by participants will be collected from the time of the first dose of study treatment, through the study and until the final study visit. Participants continuing to experience toxicity at the off study visit may be contacted for additional assessments until the toxicity has resolved or is deemed irreversible.

### 6.1 Anticipated Toxicities

The preclinical safety evaluation showed that the toxicity profile of AUY922 is dominated by cytotoxic and inflammatory reactions in the intestine, bone marrow and lymphoid tissue, as well as a moderate risk of local irritation at the injection site. The observed changes were reversible in the animal experiments. Nevertheless, there is a probability that patients may experience diarrhea following treatment with AUY922. Safety pharmacology studies revealed no effects on CNS or respiratory functions.

Based on *in vitro* and *in vivo* data, a potential for cardiovascular toxicity, such as QTc prolongation or proarrhythmia could not be completely excluded. *In vitro* cardiac safety studies demonstrated a pre-clinical signal for QT prolongation, however, no effects on QT or QTc were observed in the GLP dog and monkey telemetry studies *in vivo*. Due to potential cardiac toxicity patients in ongoing studies are undergoing careful cardiac monitoring.

No potential for genotoxicity (*in vitro* and *in vivo*) or phototoxicity (*in vitro*) was found in the preclinical safety studies conducted so far. Patients treated with this medication have had reversible ocular toxicities, see below.

In conclusion, main target organs for AUY922 are the intestine, bone marrow and lymphoid tissue. There may be a risk of QTc prolongation, of visual changes, and of a local irritative effect.

The cardiac safety parameters can be monitored in the clinic using an intensive ECG and vital signs monitoring schedule, see Section 6.2.3. Detailed instructions for the observation and treatment of diarrhea and visual toxicities are also provided in this study protocol, Sections 6.2 and 6.3. If a peripheral line is used for the infusion of the study drug, the injection site should be monitored carefully during the time of infusion.

## 6.2 Surveillance and Management of Specific Toxicities

Dose modification instructions for general adverse events are found in Section 6.3.

### 6.2.1 Diarrhea Management

In previous studies, AUY922 was shown to induce gastrointestinal toxicities in some patients and therefore there is a substantial risk that patients will develop diarrhea.

Proactively look for occurrence of diarrhea after start of AUY922 treatment. Call patients at home, if necessary, to detect diarrhea early during the first 8 weeks. If no problems occur, instruct the patient to call if and when a problem does arise.

General suggestions:

- Stop all lactose-containing products, and alcohol
- Stop laxatives, bulk fiber (i.e Metamucil®, Procter & Gamble), and stool softeners (docusate sodium; Colace, Roberts)
- Drink 8 to 10 large glasses of clear liquids per day (i.e water, Pedialyte® (Ross), Gatorade (Quaker), broth)
- Eat frequent small meals (bananas, rice, applesauce, Ensure®, toast)
- Stop high-osmolar food supplements such as Ensure Plus and Jevity Plus (with fiber)

It is recommended that patients be provided loperamide tablets and that patients are instructed on the use of loperamide at cycle 1 in order to manage signs or symptoms of diarrhea at home.

Patients should be instructed to start oral loperamide (initial administration of 4 mg, then 2 mg every 4 hours (maximum of 16 mg/day) at the first sign of loose stool or symptoms of abdominal pain. At the beginning of each cycle, each patient should be specifically questioned regarding any experience of diarrhea or diarrhea related symptoms.

#### **Treatment of diarrhea grade 1 or 2**

Diarrhea grade 1 or 2 will be treated with loperamide (initial administration 4 mg, then 2 mg every 4 hours (maximum of 16 mg/day) or after each unformed stool).

#### **24 hours after the start of diarrhea, if:**

##### **Diarrhea resolved**

- Continue dietary modifications
- Gradually add solid foods to diet
- Discontinue loperamide after 12-hour interval without diarrhea
- See Section 6.3 for dose modification recommendations upon re-initiation of AUY922

**Diarrhea unresolved**

- Addition of opium tincture or dihydrocodeine tartrate tablets/injections
- Re-assessment for dehydration, sepsis, ileus
- Medical check and selected work-up to evaluate whether patient does not need hospitalization (see below for recommended diarrhea work-up)

**48 hours after the start of diarrhea, if:**

**Diarrhea resolved**

- Continue dietary modifications
- Gradually add solid foods to diet
- Discontinue loperamide and/or other agents after 12-hour interval without diarrhea
- See Section 6.3 for dose modification recommendations upon re-initiation of AUY922

**Diarrhea unresolved**

- If persistent diarrhea (CTCAE grades 1 or 2) after 2x 24 hours with high dose loperamide and opiates, admit to hospital and follow recommendations for grade 3/4 diarrhea until resolved.

If diarrhea has progressed to CTCAE grades 3 or 4, begin measures outlined below

**Treatment of diarrhea grade 3 or 4**

Severe diarrhea grade 3 or 4 may be treated with hospitalization, high dose loperamide (initial 4 mg, then 2 mg every 2 hours) and addition of opium tincture or dihydrocodeine tartrate tablets/injections. Additionally, intravenous fluids and antibiotics may be given as needed with monitoring of the patient's condition to rule out other causes for diarrhea. Observe for response.

**24 hours after the start of diarrhea, if diarrhea is unresolved:**

- Administer subcutaneous octreotide (100-500 µg TID)
- Consider intravenous fluids and antibiotics as clinically indicated.
- If grade 3 or 4 diarrhea persists, patients should receive opium tincture or dihydrocodeine tartrate by subcutaneous or intra-muscular injection.
- If grade 3 or 4 diarrhea persists despite opium tincture or dihydrocodeine, subcutaneous octreotide (500-1000 µg TID) should be administered.
- See table 5 for dose modifications secondary to diarrhea.

### **Diarrhea work-up**

- History and physical exam.
- Examination of stool for occult blood.
- Examine the stool for fecal leukocytes.
- Examine the stool for *C. difficile* toxin if high clinical suspicion.
- Consider stool cultures for pathogens such as *Shigella* and pathogenic *E. coli*.
- Endoscopic examinations may be considered only if absolutely necessary. The bowel is likely to be fragile with evidence of colitis and thus great care and caution must be exercised in undertaking these invasive procedures.

#### **6.2.2 Ocular Toxicity Management**

Weekly administration of AUY922 may cause visual symptoms. The visual symptom descriptions from ongoing phase studies have included slow dark-light adaptation or photophobia, blurred vision, floaters and flashes in peripheral vision, dark or black spots, darkening of vision, decreased peripheral vision, color vision disturbances, and dry eye syndrome. The visual symptoms were mostly reported the day after the second or third infusion and typically resolved within a week or two weeks post dose. All visual symptoms were reversible; in some patients the events resolved with omission of a dose or after discontinuation of AUY922 treatment.

The standard recommendation for managing visual toxicities with AUY is to hold the drug if toxicities are grade 2 or higher. See Section 6.3 for dose reduction guidelines.

Standard ophthalmologic assessments will be required at baseline and follow-up exams will be conducted at the time when visual symptom(s) are reported (if any), at the beginning of cycle 3 if no visual symptom(s) are reported, and at study discontinuation.

The following standard ophthalmologic assessments are required:

1. Visual acuity test
2. Intraocular pressure test
3. Slit-lamp test
4. Dilated fundus test
5. Color-vision (Ishihara-plate) test

Additional assessments or tests may be conducted as clinically indicated. Visual symptoms will be graded using NCI CTCAE 4.0. However, for the acuity test (Snellen charts) the following grading should be applied.

**Table 2. Visual AE Grading for AUY922 Using Snellen Charts**

| Toxicity         | Grade 1                                | Grade 2     | Grade 3      | Grade 4         |
|------------------|--|-------------|--------------|-----------------|
| Decreased Acuity | Baseline-20/20 despite visual symptoms | 20/30-20/40 | 20/50-20/100 | 20/200 or below |

| Toxicity  | Grade 1 | Grade 2 | Grade 3 | Grade 4 |
|---|---------|---------|---------|---------|
| Note: Refers to the visual acuity when a patient wears his or her best eyeglasses.
The acuity scores pertains to the better eye. |         |         |         |         |

### 6.2.3 Surveillance for Cardiac Toxicities

In telemetry studies in monkeys, no clear effects on the QTc interval have been observed following administration of AUY922. But based upon *in vitro* and *in vivo* data, a potential for cardiovascular toxicity, such as QTc prolongation or proarrhythmia with AUY922 could not be excluded; therefore, cardiovascular monitoring will be conducted throughout the study.

As part of the screening process, patients will be required to undergo either a MUGA or transthoracic echocardiogram to assess left ventricular ejection fraction (LVEF). Patients will be closely monitored by ECG throughout the study, see schedule below. If cardiac changes are observed during monitoring, please refer to Section 6.3 for dose modifications.

**Table 3. Schedule for 12-lead ECG Monitoring**

| Cycle                 | Day      | 12-lead ECG | Timing and details   |
|-----------------------|----------|-------------|--|
| Baseline              | Baseline | X           | Three 12-lead ECGs.  |
| 1                     | 1        | X           | A 12-lead ECG should be obtained prior to the infusion and after infusion.                         |
|                       | 2        | X           | A 12-lead ECG should be obtained at approximately 24hrs post end of infusion.                      |
|                       | 3        | X           | A 12-lead ECG should be obtained at approximately 48 hrs post end of infusion.                     |
|                       | 8        | X           | A 12-lead ECG should be obtained at pre-infusion (timing is not pre-specified) and after infusion. |
|                       | 15       | X           | A 12-lead ECG should be obtained at pre-infusion (timing is not pre-specified) and after infusion. |
| All subsequent cycles | 1, 8, 15 | X           | A 12-lead ECG should be obtained at pre-infusion (timing is not pre-specified) and after infusion. |

### 6.3 Dose Modifications/Delays

If the patient experiences unacceptable toxicities, treatment with the study drug should be suspended until the toxicities return to  $\leq$  CTCAE grade 1 (or baseline). Dose modification may be required upon treatment resumption, see below.

Patients whose treatment is interrupted or permanently discontinued due to an adverse event or abnormal laboratory value should be followed at least once a week for 4 weeks, and subsequently at 4-week intervals, until resolution or stabilization of the event, whichever comes first. If a patient requires a dose delay of  $>21$  days from the intended day of the next scheduled dose, then the patient must discontinue the study. All patients will be followed for adverse events and serious adverse events for 28 days following the last dose of AUY922.

Toxicity will be assessed using the NCI-CTC for Adverse Events, version 4.0 (CTCAE v4.0)

For patients who are unable to tolerate the protocol-specified dosing schedule, schedule adjustments are permitted. This includes the ability to skip a week of dosing if needed up to once per cycle.

Dose reduction levels are listed in Table 4 and specific instructions for holding drug, reducing doses, and managing toxicities are listed in Table 5. Only two dose level reductions are allowed per patient.

**Table 4. Does Reduction Levels for AUY922**

| Dose reduction* |                       |                      |                      |
|-----------------|-----------------------|----------------------|----------------------|
|                 | Starting dose level 0 | Dose level – 1       | Dose level – 2       |
| AUY922          | 70 mg/m   | 55 mg/m  | 40 mg/m  |

\*Dose reduction should be based on the worst toxicity demonstrated at the last dose.  
Dose may be reduced a maximum of 2 times, no further reduction is permitted.

**Table 5. Criteria for Interruption, Dose Reduction and Re-Initiation of AUY922**

| Recommended Dose Modifications for AUY922                                |   |
|--|---|
| Worst Toxicity
CTCAE Grade a unless otherwise
specified | At any time during a cycle of AUY922
(including intended day of dosing)  |
| No toxicity   | Maintain dose level  |
| Diarrhea  |   |
| Grade 1 (see Section 6.2 for recommended treatment algorithm)            | Maintain dose level   |
| Grade 2
(see Section 6.2 for recommended treatment algorithm)         | Omit dose administration until recovery to Grade 1 or baseline, then continue AUY922 at:
- current dose level if grade 2 toxicity persisted ≤ 7 days.
- one dose level lower if grade 2 toxicity persisted > 7 days   |
| Grade 3
(see Section 6.2 for recommended treatment algorithm)         | Omit dose administration until recovery to Grade 1 or baseline then decrease the next scheduled dose by 1 dose level.   |
| Grade 4
(see Section 6.2 for recommended treatment algorithm)         | Omit dose administration until recovery to Grade 1 or baseline then:
- if grade 4 toxicity lasted ≤ 24 hours, may resume AUY922 but decrease the next scheduled dose by 1 dose level.
- In the event Grade 4 toxicity lasted >24 hours despite maximal medical attention, permanently discontinue treatment.

If grade 4 toxicity recurs upon re-exposure, permanently discontinue treatment. |

| Recommended Dose Modifications for AUY922  |   |
|---|---|
| Worst Toxicity
CTCAE Grade a unless otherwise
specified                                       | At any time during a cycle of AUY922
(including intended day of dosing)  |
| Hematological  |   |
| Neutropenia (ANC)
Grade 1 (ANC < LLN - $1.5 \times 10^9/L$ ) or
Grade 2 (ANC < $1.5 - 1.0 \times 10^9/L$ ) | Maintain dose level   |
| Grade 3 (ANC < $1.0 - 0.5 \times 10^9/L$ )  | Omit dose administration until resolved to $\leq$ grade 1,

 
• If resolved in <math>\leq</math> 7 days, then maintain dose level
 
• If resolved in <math>></math> 7 days, then decrease by 1 dose level
 
       |
| Grade 4 (ANC < $0.5 \times 10^9/L$ )  | Omit dose administration until resolved to $\leq$ grade 1, then
decrease by 1 dose level   |
| Febrile neutropenia   | Omit dose administration until resolved, then decrease by 1
dose level   |
| Thrombocytopenia   |   |
| Grade 1 (PLT < LLN - $75 \times 10^9/L$ )   | Maintain dose level   |
| Grade 2 (PLT < $75 - 50 \times 10^9/L$ ) or
Grade 3 (PLT < $50-25 \times 10^9/L$ )                                   | Omit administration dose until resolved to $\leq$ grade 1, then:

 
• If resolved in <math>\leq</math> 7 days, then maintain dose level
 
• If resolved in <math>></math> 7 days, then decrease by 1 dose level
 
 |
| Grade 4 (PLT < $25 \times 10^9/L$ )   | Omit administration dose until resolved, then decrease by 1
dose level   |
| Renal  |   |
| Serum creatinine
( $< 2 \times$ ULN)  | Maintain dose level   |
| ( $2 - 3 \times$ ULN)   | Omit dose administration until resolved to $\leq$ grade 1, then

 
• If resolved in <math>\leq</math> 7 days, then maintain dose level
 
• If resolved in <math>></math> 7 days, then decrease by 1 dose level
 
  |
| Grade 3 ( $>3.0$ baseline; $> 3.0 - 6.0 \times$ ULN) or
Grade 4 ( $> 6.0 \times$ ULN)                                | Omit dose administration and permanently discontinue patient
from study treatment  |
| Hepatic  |   |
| Bilirubin
( $< 2 \times$ ULN)   | Maintain dose level   |
| ( $2 - 3 \times$ ULN)   | Omit dose administration until resolved to $\leq$ grade 1, then

 
• If resolved in <math>\leq</math> 7 days, then maintain dose level
 
• If resolved in <math>></math> 7 days, then decrease by 1 dose level
 
  |
| Grade 3 ( $> 3.0 - 10.0 \times$ ULN)  | Omit dose administration until resolved to $\leq$ grade 1, then
decrease by 1 dose level   |
| Grade 4 ( $> 10.0 \times$ ULN)  | Omit dose administration and permanently discontinue patient
from study treatment  |

| Recommended Dose Modifications for AUY922  |   |
|---|---|
| Worst Toxicity
CTCAE Grade a unless otherwise
specified   | At any time during a cycle of AUY922
(including intended day of dosing)  |
| AST or ALT
Grade 1 (>ULN - 3.0 x ULN) or
Grade 2 (Asymptomatic with ALT >3.0 - 5.0 x
ULN; >3 x ULN with the appearance of
worsening of fatigue, nausea, vomiting, right
upper quadrant pain or tenderness, fever,
rash, or eosinophilia) | Maintain dose level   |
| Grade 3 (>5.0 - 20.0 x ULN )  | Omit dose administration until resolved to ≤ grade 1 (or ≤ grade 2 in case of liver metastasis), then 

• If resolved in ≤ 7 days, then maintain dose level

• If resolved in > 7 days, then decrease by 1 dose level

   |
| Grade 4 (> 20.0 x ULN)  | Omit dose administration until resolved to ≤ grade 1, then decrease by 1 dose level   |
| Cardiac - Prolonged QTcF interval  |   |
| During cycle 1  |   |
| Absolute QTcF ≤ 480msec   | Maintain dose level and ECG monitoring as per visit schedule.   |
| Absolute QTcF ≥ 481msec and, ≤ 500 msec   | Maintain dose level. ECG monitoring assessments should be performed for 2 additional cycles at the same frequency as in cycle 1. After the second additional cycle, ECGs for subsequent cycles will be performed as follows: 

• If ECG in the additional cycles shows no QTcF absolute ≥ 481 msec then, for subsequent cycles ECG monitoring will be performed as per visit schedule.

• If ECG still abnormal (QTcF absolute ≥ 481 msec and ≤ 500 msec) then ECG monitoring must continue at the same frequency as in cycle 1 for all subsequent cycles.

 |

| Recommended Dose Modifications for AUY922  |  |
|---|--|
| Worst Toxicity
CTCAE Grade a. unless otherwise
specified                | At any time during a cycle of AUY922
(including intended day of dosing)   |
| During any cycle
Grade 3 or QTcF $\geq$ 501 msec as identified by the investigator on the ECG. | 
Omit dose administration. Monitor patient with hourly ECGs until the QTcF has returned to <math>\leq</math> 450 msec. Further monitoring as clinically indicated. Exclude other causes of QTcF prolongation such as hypokalemia, hypomagnesemia and blood oxygenation statusb.
 
Once QTcF prolongation has resolved, patients may be re-treated at one lower dose level at the investigator's discretion. ECG monitoring must continue throughout the treatment period as follows:
 

• ECG monitoring assessments should be performed for 2 additional cycles at the same frequency as in cycle 1

• If the ECGs obtained in the first and second additional cycle (after dose reduction) are without any QTcF prolongation, then ECG monitoring in subsequent cycles will be continued as per the visit schedule.

• If the patient had an absolute QTcF <math>\geq</math> 481 msec and <math>\leq</math> 500 msec, then ECG monitoring at the same frequency as in cycle 1 will be continued for all subsequent cycles.

• Patients who experience absolute QTcF <math>\geq</math> 501 msec after one dose reduction will be discontinued from study.

 
Note: If Torsades de Pointes are observed in a patient, the patient will be discontinued from the study.
 |

| Recommended Dose Modifications for AUY922  |   |
|---|---|
| Worst Toxicity
CTCAE Grade a unless otherwise
specified   | At any time during a cycle of AUY922
(including intended day of dosing)  |
| Other adverse events   |   |
| Grade 1 or 2  | Maintain dose level   |
| Grade 3   | Omit dose administration until resolved to ≤ grade 1, then decrease by 1 dose level   |
| Grade 4   | Omit dose administration and permanently discontinue patient from study   |
| Eye disorders (see section 6.2 for Grading Table)  |   |
| Grade 1   | Maintain dose level   |
| Grade 2   | Omit dose administration until resolved to ≤ grade 1 (or baseline), then continue treatment with AUY922 at the current dose level
If visual symptoms ≥ Grade 2 recur upon re-exposure to AUY922, omit dose until resolution to ≤ Grade 1, then decrease 1 dose level |
| Grade 3   | Omit dose administration until resolved to ≤ grade 1 (or baseline), then decrease 1 dose level  |
| Grade 4   | Omit dose administration and permanently discontinue patient from study   |
| All dose modifications should be based on the worst preceding toxicity.   |   |
| If a patient requires a treatment interruption of > 21 days from the last dose of AUY922, then the patient must be discontinued from the study treatment. Patients who discontinue from the study for a study-related adverse event or an abnormal laboratory value must be followed as per protocol.   |   |
| - Up to two dose reductions are allowed. In case the patient had clinical benefit and needs more than two dose reduction, it will be discussed case by case with the sponsor  |   |
| a Common Terminology Criteria for Adverse Events (CTCAE Version 4.0)   |   |
| b Exclude other causes of QTc prolongation such has hypokalemia, hypomagnesemia and blood oxygenation status. Patients who develop hypokalemia or hypomagnesemia during the study should receive electrolyte replacement as soon as possible and should not receive further AUY922 dosing until the respective electrolytes are documented to be within normal limits. |   |

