### 3. PARTICIPANT SELECTION

#### 3.1 Eligibility Criteria

Participants must meet the following criteria on screening examination to be eligible to participate in the study:

- 3.1.1 Participants must have histologically or cytologically confirmed stage IV or recurrent non-small cell lung cancer with a documented exon 20 insertion mutation in *EGFR* (exon 20 insertion/deletion and deletion mutations will also be allowed)
- 3.1.2 Participants must have measurable disease by RECIST 1.1
- 3.1.3 Patients must have received at least one prior line of therapy for their advanced lung cancer but there is no restrictions on the maximum number of prior therapies allowed.
- 3.1.4 Age  $\geq$  18 years.
- 3.1.5 Life expectancy  $\geq$  12 weeks.
- 3.1.6 ECOG performance status  $\leq$  2 (see Appendix A)
- 3.1.7 Participants must have normal organ and marrow function as defined below:
  - Hematologic:
    - Absolute Neutrophil Count (ANC)  $\geq 1.5 \times 10^9/L$
    - Hemoglobin (Hgb)  $\geq 8 \text{ g/dL}$
    - Platelets (plt)  $\geq 100 \times 10^9/L$
  - Biochemistry:
    - Potassium within normal limits or correctable with supplements
    - Magnesium  $>$  LLN or correctable with supplements
    - Calcium (after correction for albumin level)  $>$  LLN or correctable with supplements
  - Liver and Kidney Functions
    - AST/SGOT and ALT/SGPT  $\leq 3.0 \times$  Upper Limit of Normal (ULN) or  $\leq 5.0 \times$  Upper Limit of Normal (ULN) if liver metastases are present
    - Serum bilirubin  $\leq 1.5 \times$  ULN
    - Serum creatinine  $\leq 1.5 \times$  ULN or 24-hour clearance  $\geq 50 \text{ ml/min}$

3.1.8 The effects of AUY922 on the developing human fetus are unknown. For this reason women of child-bearing potential and men must agree to use adequate contraception (hormonal or barrier method of birth control; abstinence) prior to study entry and for the duration of study participation. Should a woman become pregnant or suspect she is pregnant while participating in this study, she should inform her treating physician immediately. In addition, women of child-bearing potential must have a documented negative serum pregnancy test. The serum pregnancy test must be obtained prior to the first administration of AUY922 ( $\leq$  72 hours prior to dosing) in all pre-menopausal women and women  $<2$  years after the onset of menopause.

3.1.9 Ability to understand and the willingness to sign a written informed consent document.

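### Table 5's creatinine rows overlap when baseline is below the ULN, so one value can call for both hold-and-resume and permanent discontinuation

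*Combined protocol and SAP*

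**What the plan says.** Table 5 (Section 6.3) handles serum creatinine in three rows.

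- The first, "Serum creatinine ( $< 2 \times$ ULN", keeps the dose level.
- The second covers 2–3 × ULN. The dose is omitted until recovery to Grade 1 or better, then resumed at the same level (recovery within 7 days) or one level lower (longer).
- The third combines Grade 3, "Grade 3 ( $>3.0$ baseline; $> 3.0 - 6.0 \times$ ULN", with Grade 4 (above 6.0 × ULN). Its action is "Omit dose administration and permanently discontinue patient from study treatment".

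The first two rows carry no CTCAE grade and refer only to the ULN. The third is graded and also refers to baseline, in the limb "Grade 3 ( $>3.0$ baseline".

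Three other places bear on the point:

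- The row-selection column of Table 5 is headed by worst toxicity, in CTCAE grade unless otherwise specified. A note at the foot of the table says that modifications follow the worst preceding toxicity.
- Section 5.1.2 asks that toxicity of Grade 3 or higher resolve to Grade 1 or baseline before each weekly dose.
- Section 3.1.7 admits patients with creatinine up to 1.5 × ULN, or with adequate 24-hour clearance, so baselines below the ULN are eligible.

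**The concern.** Two rows use one scale and the third uses two. A patient who starts well below the ULN can more than triple the baseline value and still be at or below 3 × ULN. That value meets the permanent-stop row through its baseline limb and, at the same time, a lower row through its ULN range, and the actions differ. One action allows treatment to restart; the other does not.

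The stake is consistent handling of a safety stopping rule across the three clinics named in Section 13.2. Two investigators could each point to a row that literally fits the value and reach different decisions on whether the patient's treatment is over.

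**Working it through.** This is threshold logic; the plan states no figure on this point to reproduce.

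**Notation.** Let baseline be b × ULN and the current value c × ULN.

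**Rows, from Table 5:**

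- Maintain: c < 2
- Hold, then resume: 2 ≤ c ≤ 3
- Stop permanently: c > 3b or c > 3

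**Two readings are needed for the third row.** The multiplication sign before the word baseline is not printed; the limb is taken as more than 3.0 × baseline. The semicolon is taken as 'or'. Table 5 itself supports this: the AST/ALT Grade 2 cell joins an asymptomatic and a symptomatic criterion with a semicolon ("ULN; >3 x ULN with the appearance of"), and those two cannot both hold.

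**Overlap.**

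- Stop and hold: c > 3b with 2 ≤ c ≤ 3. This is non-empty when 3b < 3, that is, b < 1.
- Stop and maintain: 3b < c < 2. This is non-empty when 3b < 2, that is, b < 2/3 ≈ 0.67.
- Total width of the zone: 3 − 3b, in units of ULN.

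| Baseline (× ULN) | 3 × baseline | Stop and maintain | Stop and hold/resume | Width |
|---|---|---|---|---|
| 0.4 | 1.2 | above 1.2 to below 2 | 2 to 3 | 1.8 |
| 0.5 | 1.5 | above 1.5 to below 2 | 2 to 3 | 1.5 |
| 0.6 | 1.8 | above 1.8 to below 2 | 2 to 3 | 1.2 |
| 0.8 | 2.4 | none | above 2.4 to 3 | 0.6 |
| 0.9 | 2.7 | none | above 2.7 to 3 | 0.3 |
| 0.99 | 2.97 | none | above 2.97 to 3 | 0.03 |
| 1.0 | 3.0 | none | none | 0 |
| 1.5 | 4.5 | none | none | 0 |

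Examples at b = 0.5: a value of 1.8 × ULN is 1.8 / 0.5 = 3.6 × baseline, so it meets both maintain and stop. A value of 2.5 × ULN is 2.5 / 0.5 = 5.0 × baseline, so it meets both hold/resume and stop.

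**Alternative reading.** If the semicolon means 'and', no value meets two rows. A gap opens instead for baselines above the ULN, because values above 3 × ULN and up to 3 × baseline fall in no row: above 3.0 to 3.6 × ULN at b = 1.2, and above 3.0 to 4.5 × ULN at b = 1.5. Section 3.1.7 allows such baselines. Neither reading gives every value exactly one action.

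**Comparison.** The adjacent bilirubin rows use ULN multiples only and do not overlap. The added baseline limb is what creates the problem.

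**Link to the design.** The Section 13.2 error rates for 10 + 19 patients, with at least 1 and then at least 4 successes, recompute as 0.0468 under 5% and 1 − 0.8011 = 0.1989 under 20%, against the stated 0.047 and 0.199. Creatinine handling is not an input to either.

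**The case against.** **A precedence rule may already exist.** The column heading and the footnote both point to the worst toxicity. Only the stop row carries a grade, so a careful reader may conclude that it prevails. This has force, and the text leans that way. It does not settle the matter: those lines say which toxicity governs, not which of two definitions of the same creatinine value applies, and the two lower rows have no grade to rank against Grade 3 while stating their own ranges and actions.

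**Dosing would be withheld anyway.** A reader might infer that one site would carry on dosing while another stops the same patient for good. Section 5.1.2 largely removes that scenario: a value above 3 × baseline is Grade 3 by Table 5's own label, and Grade 3 toxicity should resolve before the next dose. This stands. It leaves open whether the patient may restart after recovery.

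**The efficacy result is not shown to be affected.** A reader might also infer that the overlap could tip the 4-of-29 decision, because a stopped patient leaves 6-weekly scanning. The documents do not support this. Footnote 7 of the study calendar has patients who stop for reasons other than progression re-staged every 12 weeks until another anti-cancer treatment begins, and recommends an end-of-treatment scan if the last was at least 4 weeks earlier. Section 9.1.4 runs stable disease from start of treatment to progression, not to the end of dosing. Section 13.6 counts all patients as evaluable for response. Scans become less frequent, but any effect on the count is speculative.

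**It may rarely arise.** Creatinine must more than triple, and the clinical summaries in Section 2.1.3 and the anticipated toxicities in Section 6.1 do not feature renal toxicity. This is fair and limits priority, but it does not make the rows consistent.

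**Conclusion.** The rows are wrong as written. With the baseline limb read as more than 3.0 × baseline and the semicolon as 'or', every baseline below 1.0 × ULN has a range of values, from above 3 × baseline to 3 × ULN, that meets the permanent-stop row and a lower row. The lower row is hold/resume throughout that set of baselines, and maintain as well when baseline is below 0.67 × ULN. The range is wide at low baselines (1.5 × ULN at a baseline of 0.5) and almost vanishes near the ULN (0.03 × ULN at 0.99).

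Given Section 5.1.2, the main unresolved conflict is whether a patient in this range may resume or must stop permanently.

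That every sub-ULN baseline has an overlap describes the thresholds, not how many patients will be affected; the documents give no expected frequency. No effect on the Simon error rates or on the 4-of-29 decision is shown. This is a lower-priority correction to a safety table.

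**What to change.** The sponsor, with its safety physician, should reconcile the three creatinine rows with each other, with Section 5.1.2 and with the worst-toxicity note, so that each value maps to one action. Two drafting routes would do this: put all three rows on one scale, or keep both scales and state which row prevails when a value meets more than one. The amended cell should also print the multiplier for baseline and replace the semicolon with an explicit 'or' or 'and'. If 'and' is intended, the gap for baselines above the ULN must be closed as well. No view is taken here on which action or threshold is right.

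The cost is a wording amendment to one table, with the approvals that Section 12.1 requires. No new tests are needed, because the study calendar already schedules chemistry, including creatinine, at baseline and at dosing visits. Sample size and analysis do not change.
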